### **9.3 Outcomes**

#### **9.3.1 Primary Outcome**

The primary outcome measures for this study will be change in MADRS scores. The MADRS is a clinical assessment tool used to rate a patient's level of depression and is the standard scale used for depression research studies. The YMRS will be used as a second primary outcome measure to assess any changes in symptoms of mania over the course of treatment. The YMRS is a clinical assessment tool used to assess the presence and severity of manic symptoms. The primary outcome measures will be assessed as the change between baseline and immediate (up to 5 days after last day of treatment) post-treatment assessment.

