propensity of antidepressant response to iTBS by modifying parameters in pulse spacing, dosage and treatment target location (Cazzoli et al., 2009, 2012; Fox et al., 2012; Gamboa et al., 2010; Noh et al., 2012). Applied in a sample of individuals with unipolar (n=20) and bipolar (n=5) treatment resistant depression (TRD), the use of an accelerated iTBS paradigm yielded approximately 90% response and remission rates in depressive symptoms, in both unipolar and bipolar TRD participants (Cole et al., 2020). Of the 5 bipolar TRD participants, all met depression remission criteria within 5 days of treatment, with no hypomania/mania conversion observed during treatment or at follow-up. More recently, SAINT demonstrated evidence of efficacy over sham stimulation in RCT for treatment-resistance depression (Cole et al., 2022). The current study aims to further evaluate the use of an adapted accelerated iTBS protocol for bipolar TRD and neuroimaging biomarkers of treatment response. It will leverage the resources of the National Network of Depression Centers (NNDC), a consortium of academic centers of excellence caring for participants with depression and bipolar disorder, to conduct the pilot study.

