## 6. STUDY PROCEDURES

### 6.1 Schedule of Evaluations

Assessment	Screening (Day -50 to Day -5)	Baseline (Day 0)	Active Study (Day 1)	Active Study (Day 2)	Active Study (Day 3)	Active Study (Day 4)	Active Study (Day 5)	Follow up: Immediate (Day 8 to Day 10)	Follow up: 1-month (Day 30 to Day 40)
Informed Consent	X								
Medical History/Records	X								
MRI Safety Form	X								
Structured Clinical Interview	X								
Clinician Administered Scales	X	X	X	X	X	X	X	X	X
Self-Rated Scales	X	X	X	X	X	X	X	X	X
Biometric Data		X	X	X	X	X	X	X	X
MRI		X						X	
Neurocognitive Measures		X						X	
Study Treatment			X	X	X	X	X		
Continue Medications	X	X	X	X	X	X	X	X	X
Monitor for Adverse Events			X	X	X	X	X		

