## 7. SAFETY ASSESSMENTS

### **Risk Assessment:**

**TMS:** Extensive published data show that this accelerated theta-burst rTMS protocol in prefrontal cortex is safe and very well tolerated (Sonmez et al., 2019). The most common side effects were mild headache, fatigue, and some discomfort at the stimulation site.

No seizures were observed in any of the above studies. However, very rarely, TMS can induce seizures (17 reported cases to date among tens of thousands of participants treated with rTMS, but few to none if proper safety and enrollment procedures are followed), with a seizure risk at approximately 1:30,000 sessions for traditional high frequency rTMS (Rossi et al., 2009). To minimize the chances of this adverse event, participants with seizure history will be excluded. The FDA has considered studies of standard TMS to be nonsignificant risk (not requiring an IDE).

Another potential immediate risk is that of induction of mania. Although there have been no such cases of mania induced by TBS, there have been at least 13 cases of rTMS-induced mania reported from fixed-frequency rTMS in participants with depression (Xia et al., 2008). The rTMS-induced mania rate reported by Xia et al was 0.84% as compared to 0.73% for sham, which were not significantly different from each other.

Another potential risk is mild pain at the site of stimulation, which occurs during stimulation only, and which wanes with each session. There is also a risk of psychological distress related to this pain, should it occur, though discomfort associated with rTMS is typically mild, and not distressing when participants are reassured it is not dangerous. For participants that continue to experience discomfort with TMS, pre-treatment with acetaminophen, ibuprofen, and/or lidocaine will be allowed as warranted. Participants and treaters will wear earplugs during all treatment sessions. In between sessions, participants will be placed in a relaxing environment to maximize psychological well-being.

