### **9.2 Early Stopping Rules**

The study will be terminated if:

Three or more participants reach hypomania as defined by a score of greater than 10 on the YMRS scale without resolution (YMRS <10) within 24 hours with pharmacologic measures as outlined above.

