## 9.4 Data Analyses

The primary outcome measures will be analyzed using generalized linear mixed models to test if there are significant changes in scores over follow-up. Based on previous work, we will use a compound symmetry or autoregressive covariance structure (based on distribution of residuals) and robust estimation of coefficients to handle violations of model assumptions. Random effects will be included to account for repeated measures on the same participants, and fixed effects of time will be evaluated controlling for fixed effects of age, sex and number of days to reach treatment remission. All post hoc pairwise comparisons will be Bonferroni corrected. Exploratory endpoints related to biometrics will be analyzed in similar fashion.

For assessment of the secondary outcome measures of change in functional connectivity, we will employ a resting-state seed-based functional connectivity approach to assess connectivity between the subcallosal cingulate connectivity to the DLPFC and within the default mode network. For each participant, the correlation coefficients between average blood oxygen level-dependent (BOLD) time series of the seed-region and the BOLD time series of each grey matter voxel within the DLPFC or default mode network will be calculated. The correlation coefficient will be converted to normally distributed z scores by the application of Fisher's r to z transformation. The resulting connectivity maps will be analyzed with repeated measures ANOVA to compare pre-iTBS vs post-iTBS connectivity measures as a within-subject variable, and sex and site as a between-subject covariate.

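### The YMRS primary outcome scores mania resolved by the immediate visit as no change, and no listed outcome counts the participants affected

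*Combined protocol and SAP*

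**What the plan says.** Section 9.3.1 gives the YMRS its purpose: "The YMRS will be used as a second primary outcome measure to assess any changes in symptoms of mania over the course of treatment". The same section says that both primary outcomes, MADRS and YMRS, are "assessed as the change between baseline and immediate (up to 5 days after last day of treatment) post-treatment assessment". Section 9.4 analyses them with generalized linear mixed models "to test if there are significant changes in scores over follow-up", without listing the visits that enter.

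The YMRS is rated at baseline, morning and evening on each treatment day, and at both follow-up visits (6.2). Emergent mania is defined by an item rule: a rise of at least 2 points on each of two or more YMRS items. When it occurs, stimulation stops and the symptoms are treated (5.1, 6.2, 7.1, 7.2).

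The outcomes in 1.1, 9.3.1 and 9.3.2 are MADRS change, YMRS change, functional connectivity and biometrics. Section 9.2 does count participants, but to decide on ending the study. It requires three or more with "a score of greater than 10 on the YMRS scale without resolution" within 24 hours. Section 7.3 sends adverse events to the IRBs and the device manufacturer and plans no summary. In the 6.1 schedule, the row "Monitor for Adverse Events" is marked on Days 1 to 5 only.

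The protocol states its own background evidence on this risk as cases. Section 2.2 reports 5 bipolar participants "with no hypomania/mania conversion observed during treatment or at follow-up". The risk assessment in Section 7 gives an rTMS-induced mania rate that "was 0.84% as compared to 0.73% for sham".

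**The concern.** The stated purpose covers the whole course of treatment, but the measurement is taken at one point after it. For mania that arises on a treatment day, the protocol's own response falls between the event and the measurement. The better that response works, the less of the event remains to be measured. The analysis could therefore report no mean change in YMRS although several participants had had stimulation stopped for emergent mania.

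The abstract says the pilot should lead to a larger, adequately powered study, and 9.1 says it should supply preliminary data. For emergent mania in bipolar I disorder, the useful planning quantity is how many participants were affected. The outcome list does not provide it.

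**Working it through.** **Inputs from the documents.** N = 2 sites x 5 = 10, which agrees with the synopsis. The plan gives no expected YMRS change, standard deviation or mania rate for this trial, so it has no figure of its own to reproduce here. The smallest total rise that meets the item rule is 2 items x 2 points = 4, if the other items are unchanged.

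**Assumed for illustration.** Baseline YMRS of 3, a 12-point peak on Day 3, and an immediate visit on Day 9.

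**1. The defined contrast.** If k of 10 participants rise by d points and a fraction f of the rise remains at the visit, the others being unchanged, the mean change is k x d x f / 10.
- k = 2, d = 12: f = 1 gives 2.4; f = 0.5 gives 1.2; f = 0 gives 0.
- One participant with the minimum 4-point rise, fully persistent: 4/10 = 0.4.

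**2. If daily ratings enter the 9.4 model.** I took complete data on Days 0 to 5 and Day 9, one rating per day, correlation 0.5, an identity link and no covariates. A resolved Day 3 rise was given to k = 0, 1, 2 or 3 participants.
- Time as categories: the baseline-to-immediate contrast is 0.0 for every k, under both compound symmetry and AR(1). The Day 3 minus baseline contrast is 1.2, 2.4 and 3.6 for k = 1, 2 and 3.
- Linear time: the fitted change over 9 days is about -0.05 to -0.26 for k = 1 to 3, so resolved rises look like a slight fall.
- The plan also specifies "robust estimation of coefficients to handle violations of model assumptions". Read as robust standard errors, this leaves these contrasts unchanged.

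**3. The stopping rule does not supply the count.** From the assumed baseline of 3, a minimum item-rule case reaches 3 + 4 = 7, below the 9.2 threshold of 10. Cases above 10 that resolve within 24 hours are also excluded.

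**4. What a count would give.** Exact (Clopper-Pearson) 95% limits:

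| Affected | Limits |
|---|---|
| 0/10 | 0 to 30.8% |
| 1/10 | 0.3 to 44.5% |
| 2/10 | 2.5 to 55.6% |
| 3/10 | 6.7 to 65.2% |

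The earlier 0/5 has limits of 0 to 52.2%. At a true rate of 0.84%, the chance of at least one case in 10 is 1 - (1 - 0.0084)^10 = 8.1%.

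**5. False counts from repeated ratings.** Scheduled ratings after the first session number 1 on Day 1 (evening), 8 on Days 2 to 5 and 2 at follow-up, or 11 in all. If each rating falsely meets the rule with assumed probability p, independently, the chance per participant is 1 - (1 - p)^11. This is 5.4%, 10.5% and 19.9% for p = 0.5%, 1% and 2%, or about 0.5 to 2 participants in 10.

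**The case against.** The strongest reply is that nothing is lost. Every item-rule case stops stimulation, adverse events are reported, item scores are collected twice daily, and in 10 participants the tally is almost automatic. This stands in part. A reader might infer that safety monitoring is deficient, and the documents do not support that. Nor does the schedule's Day 1 to 5 marking mean that mania goes unobserved afterwards. YMRS and CGI-BP are scheduled at both follow-up visits, AS-18 and digiBP are completed there by responders and remitters, and Section 8 provides for follow-up of participants withdrawn for treatment-related reasons.

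A reader might also infer that the change score cannot see mania at all. That goes too far. Symptoms that begin after the last session cannot stop stimulation and may be present at the immediate visit. That visit can also come soon after treatment stops, so some episodes would persist to it. Both kinds are captured, though averaged over 10 participants. How many episodes would have resolved is unknown.

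Section 9.4 may admit the daily ratings. If so, day-by-day contrasts could show a mean rise during treatment, and missing immediate visits would give those ratings some indirect weight. Neither yields a number of participants.

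Finally, an item-rule count should not be read as directly comparable with the 0 of 5 or the 0.84%. The rule may capture milder changes than those figures do, and the documents do not give the case definitions behind them.

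**Conclusion.** The point holds as a gap in outcome definition and reporting. An episode that starts on a treatment day and has fully resolved by the immediate visit contributes exactly 0 to the YMRS primary outcome. This is arithmetic and needs no assumption about peak height. Adding treatment-day ratings to the model leaves the defined contrast unchanged, given complete data and time as categories. No listed outcome counts the participants affected.

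The practical size depends on how many episodes arise and how many resolve in time, and the documents give neither. The 12-point peak, the visit days, the correlation and the false-positive rates are assumptions. The remedy has limited precision, since even 0 of 10 is compatible with a rate of up to 30.8%. The change should be made because it costs little and the stated contrast alone could report no mania signal despite cases. Confidence is medium.

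**What to change.** In 9.3.1 and 9.4:

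- Keep the YMRS change score, and state which ratings (morning and evening, immediate, 1-month) enter the mixed model and how time is coded.
- Report descriptively the number and proportion of participants who meet the item rule at any scheduled or unscheduled YMRS after the first session through the 1-month visit, with an exact 95% confidence interval. For this analysis only, measure the rise from Day 0; the documents name no reference rating, so this is a choice made here.
- List each participant's maximum YMRS increase.
- Show separately the participants whom a clinician judged to have emergent mania or hypomania, leaving out stops on clinician judgment for other reasons.
- State beside the table that the count is imprecise, is pushed upward by repeated ratings, and may not be comparable with the figures in 2.2 and the Section 7 risk assessment.

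The definition must also be reconciled across sections. Section 5.1 includes clinician judgment in it, 6.2 and 7.2 list that judgment as a separate ground for stopping, and the item rule in 7.1 omits it.

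The cost is some wording and one table, because the ratings are already collected. The drawback is the false-count inflation shown above, which also affects the maxima, so both should stay descriptive.

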## STUDY SYNOPSIS

Title	A Pilot Study of iTBS in Bipolar I Depression
Source of Funding	Baszucki Brain Research Fund
Study Population	Participants aged 18+ years old with a diagnosis of bipolar I disorder, current episode depressed
Study Design	A multisite, open label pilot study to investigate the efficacy and safety of a novel accelerated intermittent theta-burst stimulation (iTBS) protocol while assessing for changes in neuroimaging biomarkers associated with treatment response
Primary Objectives	To examine the use of accelerated iTBS to treat symptoms of treatment resistant depression in bipolar I disorder and assess changes in neuroimaging biomarkers that may predict treatment response.
Number of Sites	2
Total number of Participants	10 (5 at each site)
Study Duration	1 year

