## 1. STUDY OBJECTIVES

### 1.1 Primary Objective

To examine the use of accelerated iTBS to treat symptoms of treatment resistant depression in bipolar I disorder and assess changes in neuroimaging biomarkers that may predict treatment response:

Primary Outcome Measure: Change in Montgomery-Asberg Depression Rating Scale (MADRS) score.

Secondary Outcome Measure: Changes in MRI derived functional connectivity of the subcallosal cingulate to the DLPFC and within the default mode network.

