## **9. STATISTICAL CONSIDERATIONS**

### **9.1 General Design Considerations**

This is an open label pilot study. The study will not include blinding given that this is a single group assignment to treatment. Study will not include a placebo or non-treatment group as this is a feasibility pilot study.

The sample size for this pilot study was selected to allow for a sufficient evaluation of the feasibility of carrying out the protocol across multiple NNDC centers given the available resources and provide preliminary data to motivate further study of this treatment approach.

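### YMRS is a primary outcome in 9.3.1 but not in 1.1, and its only planned analysis, a test for change in 10 people, says little about whether mania symptoms worsened

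*Combined protocol and SAP*

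**What the plan says.** Section 1.1 gives a single primary measure: "Primary Outcome Measure: Change in Montgomery-Asberg Depression Rating Scale (MADRS) score". Section 9.3.1 also starts from MADRS but then states: "The YMRS will be used as a second primary outcome measure to assess any changes in symptoms of mania over the course of treatment". Both sections are current text, so this is not a leftover from the revision history.

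Section 9.3.1 fixes the contrast for both measures: "The primary outcome measures will be assessed as the change between baseline and immediate (up to 5 days after last day of treatment) post-treatment assessment". Section 9.4 says the primary outcomes will be analysed with "generalized linear mixed models to test if there are significant changes in scores over follow-up". It gives no alpha, sidedness, margin or confidence-interval criterion. It plans no count of participants with treatment-emergent mania, and no rule says how the two primaries are read together. The only multiplicity statement is "All post hoc pairwise comparisons will be Bonferroni corrected", which does not cover two primary outcomes.

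The study has 10 participants, five per site (Synopsis). Section 9.1 explains the number: "The sample size for this pilot study was selected to allow for a sufficient evaluation of the feasibility". There is no control arm: "Study will not include a placebo or non-treatment group as this is a feasibility pilot study".

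**The concern.** The set of primary outcomes depends on which section is read. The two measures also ask different questions. For MADRS a change is the hoped-for result, so a test for change fits. For YMRS the hoped-for result is no worsening, and failing to find a significant change in 10 people does not show that.

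A mean is also a poor summary of a hazard that may strike one to three participants and leave the rest unaffected. The timing adds to this. Section 9.3.1 wants YMRS to describe mania symptoms during treatment, but the endpoint is one visit after treatment ends. Under 5.1, 6.2, 7.1 and 7.2, a participant with emergent symptoms is taken off stimulation and treated for them at onset. The change score may then no longer show the episode.

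The Synopsis names safety as well as efficacy as a purpose of the study, so the primary YMRS result is likely to be quoted.

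**Working it through.** **Inputs.** From the documents: n = 10; contrast baseline to immediate post-treatment; analysis by a test for change. Not in the documents, so assumed: two-sided 5%, no dropout, and a paired t test as a simple stand-in for the mixed-model time effect. The sample size has no power calculation behind it, so there is no figure of the plan's own to reproduce.

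**Step 1: power for a shift in the mean.** With d the true mean change divided by the SD of change, power is that of a noncentral t with 9 degrees of freedom and noncentrality d√10. The critical value is 2.262.

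| True mean rise (SD) | Two-sided 5% | Two-sided 2.5% |
|---|---|---|
| 0.3 | 14% | 8% |
| 0.5 | 29% | 19% |
| 0.8 | 62% | 48% |
| 1.0 | 80% | 68% |

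A one-sided 5% test would give 43% at 0.5 SD.

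**Step 2: what a null result leaves open.** The 95% interval half-width is 2.262/√10 = 0.72 SD. If the SD of YMRS change were 2 to 3 points (assumed), that is about 1.4 to 2.1 points, and 0.5 SD is 1 to 1.5 points.

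**Step 3: a rise in a few participants.** Let k of 10 rise by the same amount a and the rest not change. The mean is ka/10 and its standard error is a√(k(10−k))/30. Hence t = 3√(k/(10−k)), and a cancels: the size of the rise does not matter.

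| k | t | p (two-sided) |
|---|---|---|
| 1 | 1.00 | 0.34 |
| 2 | 1.50 | 0.17 |
| 3 | 1.96 | 0.08 |
| 4 | 2.45 | 0.04 |

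Adding noise does not rescue the test. In a simulation (20,000 runs per scenario; SD 2 to 3 points, rises of 8 to 16 points in those affected, mean change zero in the others), the chance of a significant increase was 0.2% to 4% with one affected, 1% to 9% with two and 13% to 19% with three. If the others improved by 1 point on average, it was at most about 4%.

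**Step 4: would a mean with an interval be enough?** Take k = 1 and a = 12. The mean is 1.2, the standard error 1.2, and the 95% interval 1.2 ± 2.262 × 1.2, or about −1.5 to 3.9. One clear case is diluted here too, so a count is needed beside the mean.

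**Step 5: what a count would show.** Exact (Clopper-Pearson) 95% intervals:

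- 0/10: upper limit 1 − 0.025^(1/10) = 30.8%
- 1/10: 0.3% to 44.5%
- 2/10: 2.5% to 55.6%

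Even a clean result would not exclude a rate of about 3 in 10, and the interval makes that plain.

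**The case against.** The strongest reply is that mania is not left to this test. YMRS is taken morning and evening on each treatment day (6.2), with a modified PANAS between sessions. An item-level rule discontinues treatment (5.1, 6.2, 7.1, 7.2), a study-level rule stops the trial (9.2), and all adverse events are reported (7.3). A reader might infer from the weak test that mania would go unnoticed. The documents do not support that: individual cases would be detected, acted on and reported whatever the model's p-value. But these rules govern care and termination, and none says how mania is analysed in the results.

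A reader might also infer that the plan treats a non-significant YMRS change as proof of safety. It nowhere says so; 9.3.1 gives YMRS a neutral descriptive purpose.

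Two primaries tested at 5% would give a familywise error of 1 − 0.95² = 9.75% if independent. That needs a rule that either outcome suffices, which the plan does not contain, so no weight is put on it.

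It is fair to say that a feasibility pilot need not be powered and that a second, safety primary is a legitimate choice. Both points stand. They explain the sample size and allow YMRS to stay primary, but they do not resolve the mismatch with 1.1. A pilot purpose favours estimation over a significance test.

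Finally, the power figures come from a paired t test and not from the mixed model with covariates, and missing a mean shift of 1 to 1.5 points may not matter clinically. Both are fair cautions. The result for a few affected participants does not depend on the SD or on the size of the rise.

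**Conclusion.** The point holds in limited form. Sections 1.1 and 9.3.1 conflict on the primary outcomes, and the only analysis planned for YMRS is a test poorly suited to a safety question. Under the assumed paired t test at two-sided 5%, a mean rise of 0.5 SD would be missed about 71% of the time. Equal rises in 3 of 10 participants, with no change in the rest, would still give p of about 0.08. Reading the endpoint after emergent symptoms have been treated could hide an episode further. The consequence is that the primary YMRS result could be misread as reassurance; neither undetected mania nor an intended claim of safety follows from the documents. This should be fixed before the data are analysed, but it does not call the pilot itself into question.

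**What to change.** Make 1.1 and 9.3.1 agree. Either of two routes works: MADRS as sole primary with YMRS as the key safety outcome, or YMRS listed as primary in both sections with its role stated.

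In 9.4, replace the YMRS significance test with:

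- (a) the number of participants meeting the protocol's own definition of treatment-emergent mania at any assessment, with an exact 95% interval;
- (b) each participant's maximum YMRS change from baseline;
- (c) the mean YMRS change with its 95% interval.

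State that a non-significant change will not be read as absence of mania risk. For (a), say which wording is counted: 5.1 includes clinician judgment within the definition, while 6.2 and 7.2 list it separately.

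The cost is a few sentences and a less favourable safety statement, since even 0/10 carries an upper limit of 30.8%. No new data are needed: YMRS is already scheduled at baseline, twice daily on treatment days and at both follow-up visits (6.2).
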